#### 9.0 Procedures Involved

#### 9.1 Study Design

We will conduct a single-site pilot randomized trial in 60 HCT survivors to assess the feasibility and preliminary efficacy of the intervention for improving patient-reported sexual function, QOL, and mood. Patients will be randomized in 1:1 fashion and stratified by transplant type (autologous vs. allogeneic) to either receive only a sexual health visit with a transplant clinician specializing in sexual health or a sexual health visit with a transplant clinician specializing in sexual health with access to the app. This visit may be in clinic or conducted via secure video-based conference. As transplant type is an important variable that affects sexual function and recovery post-HCT, we will stratify by HCT type to ensure balanced representation between the study groups. Both study groups will attend a visit with a transplant clinician specializing in sexual health who will conduct a brief examination and assess the need for any treatments or medications to address sexual health problems; this visit may be in clinic or conducted virtually via secure video-based conference.. The intervention group will have access to the mobile app. We will also conduct qualitative interviews with 10 patients that are randomized to the mobile app intervention, in order to understand and assess patient experience using the app. Qualitative interviews will be conducted in clinic, or over the telephone.

#### 9.2 Procedures

We will recruit 60 patients 3 months after autologous or allogeneic HCT who report having sexual dysfunction causing distress for this study. The research assistant (RA) will review the consent form with potential participants and obtain verbal or written informed consent. Upon study enrollment, participants will complete baseline study measures and then they will be randomized to the mobile app versus enhanced standard care.

**Intervention Arm:** Patients randomized to the intervention will first meet with a transplant clinician, in clinic or via secure video-based conference, for a brief medical examination to assess the need for medications for erectile dysfunction, vaginal atrophy, or vulvovaginal GVHD given their prevalence in this population. We will then provide patients with a tablet computer that they will use to access the mobile app. We chose to use tablet computers for intervention delivery in this proof-of-concept study. However, the mobile app can be further adapted in the future to be delivered via mobile phones to enhance dissemination. Upon study enrollment, the RA will provide patients with a comprehensive tutorial and detailed instructions regarding how to use the app, in person or via secure video-based conference. The RA will encourage patients to engage their partners with the app content. The app will also prompt patients to engage their partners with specific exercises. Given the pilot nature of this study, we will not measure the effect of the intervention on partners. Patients will complete the intervention modules at their desired pace over 8 weeks. The app will prompt patients with reminders to complete their modules and utilize incentives to enhance patient engagement, as noted previously. The mobile app

will collect data on intervention fidelity (the number of completed modules, proportion of each module completed, time spent on each module, partner engagement with each module). Participants will complete additional surveys 8 and 12 weeks after clinician consult and examination.

Additionally, we will conduct qualitative interviews with 10 patients who are randomized to the intervention arm, to understand their experience of using the application and to assess patient opinions regarding the app. We will purposefully sample patients to ensure adequate representation based on age and sex. If we see different themes emerge based on age/sex, we will amend the protocol to increase our sample size for these qualitative interviews. We have developed a semi-structured qualitative interview guide to explore 1) patients' general experience using the SHIFT app and 2) patients' opinions regarding app content (Appendix M). Qualitative interviews will be conducted after patients complete all of their quantitative study assessments. Trained study staff will conduct and audio-record one-on-one interviews with patients via telephone or in-person. The estimated time to complete the patient qualitative interview is approximately 30 minutes. Audio recordings of the qualitative interviews will be stored for six months following interview completion.

Enhanced Standard Care: Patients assigned to the enhanced standard care group will not receive the mobile app. However, they will meet with a transplant clinician for a brief medical examination to assess the need for medications for erectile dysfunction, vaginal atrophy, or vulvovaginal GVHD; this visit will be conducted in clinic or virtually via secure video-based conference. The treating transplant clinician may refer patients to a psychologist, urologist, or gynecologist at the patients' request or at their discretion. At MGH, < 1% of transplant survivors are referred to a specialist to address sexual health concerns. Importantly, we did not see an increase in rate of referral to specialists during our pilot study. We will also collect data on referrals to specialists in both study groups. Although most transplant practices across the country do not systematically screen or treat sexual dysfunction, we chose a conservative control group to allow us to most accurately assess the effect of the mobile app.61 Participants will complete additional surveys 8 and 12 weeks after clinician consult and examination.

Institutions will register eligible participants in the Clinical Trials Management System (CTMS) OnCore as required by DF/HCC SOP REGIST-101.

Once the patient has been registered, a member from of the MGH Cancer Outcomes Research Program (CORe) team (independent from the study staff) will perform randomization procedures using a computer-generated randomization schema, stratified by study site and transplant type.

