## 8.0 Study Endpoints

- 8.1 Primary endpoint: The primary endpoint of this pilot RCT is to assess the feasibility of the intervention. The proposed intervention app will be deemed feasible if at least 60% (95% CI +/- 12%) of eligible patients are enrolled in the study, and of those enrolled, at least 60% engage with at least 70% of the intervention modules. Modules engagement will be captured by the app.
- 8.2 Secondary endpoints:
  - Compare patient-reported global satisfaction with sex (PROMIS Sexual Function and Satisfaction Measure) scores at 8 weeks between the study groups
  - Compare patient-reported interest in sexual activity (PROMIS Sexual Function and Satisfaction Measure Interest in sexual activity domain) scores at 8 weeks between the study groups
  - Compare patient-reported global satisfaction with sex (PROMIS Sexual Function and Satisfaction Measure Global satisfaction with sex domain) at 12 weeks between the study groups
  - Compare patient-reported interest in sexual activity (PROMIS Sexual Function and Satisfaction Measure Interest in sexual activity domain) at 12 weeks between the study groups
  - Compare patient-reported orgasm (PROMIS Sexual Function and Satisfaction Measure Orgasm domain) at 8 weeks and 12 weeks between the study groups
  - For males: compare patient-reported erectile function (PROMIS Sexual Function and Satisfaction Measure Erectile function domain) at 8 and 12 weeks between the study groups

- For females: compare patient-reported lubrication and vaginal comfort (PROMIS Sexual Function and Satisfaction Measure lubrication and vaginal comfort domains) at 8 and 12 weeks between the study groups
- Compare patient reported QOL (FACT-BMT) at 8 and 12 weeks between the study groups
- Compare patient reported anxiety and depression symptoms (HADS) at 8 and 12 weeks between the study groups

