#### **GENERAL EXPERIENCE**

1. How difficult was it to use the SHIFT app?

I will begin by asking about your general experience using the SHIFT mobile app.

A. Difficult

B. Not Difficult

C. Not sure

C. Not sure

2. How helpful was the SHIFT app in addressing your sexual health and intimacy concerns?

A. Helpful Additional Comments:

B. Not helpful

C. Not sure

3.	What d	lid you like most about	the SHIFT app?
4.	What d	lid you like least about	the SHIFT app?
5.	How sa	atisfied were you with t	the mobile app format overall?
	A.	Satisfied	Additional Comments:
	B.	Not Satisfied	
	C.	Not sure	
6.		this study, you accesses an i-pad to access the ap	ed the SHIFT mobile app using an i-pad. How convenient was it pp?
	A.	Convenient	Additional Comments:
	B.	Not convenient	
	C.	Not sure	
7.	Did yo	u experience any techn	ical difficulties while using the SHIFT app?
	A.	Yes	Additional Comments:
	B.	No	
	C.	Not sure	

8.	How do	o you feel about the ler	ngth of the modules in the SHIFT app?
9.		did not complete the SI te the entire SHIFT ap	HIFT app, were there any reasons that made you decide to not p?
10.		o you feel about the du te the app modules?	ration of the allotted 8-week period over which you were to
	A.	Too long	Additional Comments:
	B.	Too short	
	C.	Just right	
11.		shout the SHIFT app, y were these games?	ou may have played games to reinforce your learning. How
	A.	Helpful	Additional Comments:
	B.	Not helpful	
	C.	Not sure	
12.	How do	o you feel about the fre	equency of the games in the SHIFT app?
	A.	Too little	Additional Comments:

PROTOCOL TITLE: Pilot Study of a Sexual Health Intervention Mobile Application (app) to Address Sexual Dysfunction in Hematopoietic Stem Cell Transplant Survivors
B. Just right C. Too much
13. What were the games that you liked the most in the SHIFT app?
14. What were the games that you liked the least in the SHIFT app?
15. How could we modify the SHIFT app to increase your engagement with the content?
APP CONTENT  Now I am going to ask some questions about the specific material covered in the app. We would like to ask you your opinion about the content of the app:
1. Education about sexual health and intimacy The app included educational content regarding the causes of sexual health problems after transplant and expected trajectory of sexual health recovery.
A. How helpful was it to have this educational content?
A. Helpful Additional Comments:

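### Interviewees are selected on age and sex but not on app engagement, and patients who stop the surveys have no described route to interview, so reasons for non-completion may be under-represented

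*Combined protocol and SAP*

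**What the plan says.** Section 9.2 (Procedures) sets the size and source of the interview sample: "we will conduct qualitative interviews with 10 patients who are randomized to the intervention arm". The sampling rule is "We will purposefully sample patients to ensure adequate representation based on age and sex", and the one stated reason to enlarge the sample has the same basis: "If we see different themes emerge based on age/sex, we will amend the protocol to increase our sample size for these qualitative interviews". On timing it says "Qualitative interviews will be conducted after patients complete all of their quantitative study assessments". Under the schedule in section 9.4, the last of these falls at week 12, plus or minus one week.

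Three other places bear on this:

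- Section 8.1 makes engagement one of the two parts of the feasibility endpoint: "of those enrolled, at least 60% engage with at least 70% of the intervention modules". The other part is enrolment of eligible patients.
- Section 9.2 has the app record, among other things, "the number of completed modules, proportion of each module completed, time spent on each module".
- Appendix M, General Experience, item 9 asks patients who did not finish the app "were there any reasons that made you decide to not" complete it. Item 15 asks how the app could be changed to raise engagement.

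Section 1.2 gives the aim of the interviews as exploratory: general perceptions of the app and overall satisfaction. Neither section 9.2 nor section 13.0 (Withdrawal of Subjects) describes an exit interview.

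**The concern.** The interview guide contains questions that patients with low engagement are best placed to answer, and the trial will hold a record of who those patients are. The sampling rule does not use it. The timing sentence, read literally, also makes completion of every survey a condition of interview, so a patient who misses week 8 or week 12 cannot be reached.

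If patients who use the app little also return fewer surveys, the 10 interviews will lean towards those who used it well. Reported satisfaction could then look better than it is across the app arm, and items 9 and 15 would be answered by few of the people they most concern. Low use is foreseeable: section 2.3 acknowledges poor adherence in some mobile interventions, and section 24.2 tells patients that they may skip modules they find distressing.

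**Working it through.** The plan states no figure on this point, so there is nothing to reproduce. The calculation below is an illustration.

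**Inputs from the documents**

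- 60 patients randomised 1:1 (section 9.1), taken as 60 / 2 = 30 in the app arm.
- 10 interviews, app arm only (section 9.2).
- Engagement target: 60% reach at least 70% of modules (section 8.1). I apply it to the app arm, since only that arm has the app. Exactly at target, 0.60 × 30 = 18 patients reach the level and 30 − 18 = 12 do not.

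**Assumptions**

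- The share L of the 12 who do not finish the surveys is not given, so it is run from 0% to 100%.
- All 18 engaged patients finish the surveys.
- Selection on age and sex is unrelated to engagement, so the 10 behave like a simple random draw from those who finished the surveys.

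**Formulas**

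- Low engagers available: k = 12 × (1 − L). Pool: M = 18 + k.
- Expected low engagers among 10 = 10 × k / M.
- Chance of none = C(18,10) / C(M,10). The chance of two or fewer comes from the same hypergeometric distribution.

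| L | k | M | Expected of 10 | Chance of none | Chance of two or fewer |
|---|---|---|---|---|---|
| 0% | 12 | 30 | 4.0 | 0.1% | 11.7% |
| 25% | 9 | 27 | 3.3 | 0.5% | 24.4% |
| 50% | 6 | 24 | 2.5 | 2.2% | 50.6% |
| 75% | 3 | 21 | 1.4 | 12.4% | 91.0% |
| 100% | 0 | 18 | 0 | 100% | 100% |

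For example, at L = 50%, the expected number is 10 × 6 / 24 = 2.5 and the chance of none is 43,758 / 1,961,256 = 2.2%.

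**If the engagement target is clearly missed.** With 18 of 30 below the level and L = 50%, k = 9 and M = 12 + 9 = 21. The expected number is 10 × 9 / 21 = 4.3, and the chance of none is C(12,10) / C(21,10) = 66 / 352,716 = 0.02%.

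**Reading.** Low engagers are nearly absent only if most of them also abandon the surveys. Representation does thin out as L rises: at 50% loss, about half of such draws contain two or fewer. Patients who do not finish the surveys contribute no interviews in any row, by the literal wording of the timing sentence.

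**The case against.** A reader might infer that low engagers are largely shut out of the interviews, or that a missed engagement target could not be explained. The documents do not support either reading. The entry condition is survey completion, not module completion, so a patient who opened few modules but returned the surveys can be interviewed. The surveys are light: in person, by email or by telephone (section 9.3.2), by mail (Appendix H), and about 20 minutes by telephone (Appendix I). Item 9 shows that the authors expected to interview people who had not finished. In the clear-failure case above, low engagers still supply about 4 of 10 interviews at 50% loss. App logs, and the System Usability Scale at week 8, also bear on engagement, though survey non-responders miss the latter.

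Two further points have force. The stated aim is perceptions and satisfaction, not explaining a feasibility result. And the timing sentence may be meant only as sequencing, so that interviews cannot influence the week-12 outcomes.

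What remains is narrower. Engagement is not a sampling variable although it is recorded, and no interview is described for those who stop the assessments. If sequencing is all that is meant, the text should say so. Even for perceptions and satisfaction alone, a sample tilted towards engaged patients would be a biased one.

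**Conclusion.** The point holds as a minor one about the exploratory aim. Nothing in section 9.2 ensures that patients below 70% of modules are among the 10, and patients who stop the assessments have no described route in. Views of the app and reasons for not finishing it may therefore be drawn disproportionately from engaged patients.

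How far cannot be determined, because the documents give neither an attrition rate nor the overlap between low engagement and survey loss. The illustrated range is 4.0 of 10 expected interviews down to none, and it depends on the assumed loss and on selection being otherwise unrelated to engagement. The feasibility estimate and the efficacy analyses are unaffected.

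**What to change.** Keep 10 interviews and change section 9.2 in two ways:

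1. Add app-logged module completion (below 70% versus at least 70%) to age and sex as a purposive sampling variable, aiming for several patients below 70% as numbers allow. A fixed quota is unwise: if 90% of the arm reached the level, only 0.10 × 30 = 3 patients would fall below it, so a quota of 4, for instance, could not be filled.
2. Allow the interview once the week-12 window has closed, even if surveys are incomplete, for patients who have not withdrawn and agree to be contacted. This still keeps interviews after the outcome assessments.

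The cost is a short amendment to the text and more contact attempts for low engagers; telephone interviews are already permitted. Age and sex coverage also becomes thinner. If each variable is split in two, the cells rise from 4 to 8, and the average falls from 10 / 4 = 2.5 to 10 / 8 = 1.25 interviews per cell. Patients who withdraw fully will still be missed, and the report should give the engagement level of those interviewed alongside that of the whole app arm.

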#### 9.3 Procedure to Lessen Risk

#### 9.3.1 Procedures to Lessen Risk

We do not anticipate that participation in this study will pose risk to patients other than the risk of breach in confidentiality. Prior studies of psychoeducational apps demonstrated that patients utilize the apps without any adverse emotional reactions. Should a participant express distress while using the app or completing study assessments or qualitative interview, the RA will reassure the participant that they can stop using the app and they need not answer any of the assessment questions which they find upsetting. The RA will also remind the participant that study participation is voluntary. If participants remain distressed, both the Principal Investigator and the oncology clinician will be notified. Additionally, we will offer participants who remain distressed an opportunity to meet with either the principal investigator ([name]) or a clinical psychologist ([name], a co-investigator) to help address their distress.

We will prevent breaches in confidentiality by keeping participant data on password protected Partners computers and in a locked office on MGH campus. Data logged online will be saved in password protected documents. Only study team will have access to the data.

The MGH research team will meet on weekly basis throughout the study period and will discuss any issues or concerns that may arise regarding the study procedures. Should the protocol require modifications or amendments based on these meetings, the PI will make the necessary changes and submit them to the DF/HCC IRB for approval.

#### 9.3.2 Source Records

We will administer the following measures at baseline prior to randomization, 8 weeks, and 12 weeks from the time of clinician consult and examination:

- Demographic Questionnaire (only at baseline): Participants will self-report their age, sex, race/ethnicity, marital status, religion, and education. [Appendix B]
- **Sexual Function:** We will utilize the PROMIS-2 Sexual Function and Satisfaction Measure including the following domains: global satisfaction with sex life, interest in sexual activity, and orgasm.  For men, we will also include the erectile function domain. For women, we will also administer the lubrication and vaginal comfort domains. [Appendix C]
- **QOL:** We will use the Functional Assessment of Cancer Therapy-Bone Marrow Transplant (FACT-BMT) to assess QOL. [Appendix D]
- **Mood:** We will use the Hospital Anxiety and Depression Scale (HADS) to assess symptoms of depression and anxiety during the past week in all study participants. [Appendix E]
- Usability of mobile app (only those randomized to intervention): We will use the system usability scale at eight weeks post-intervention to assess the usability of the mobile app. [Appendix F]
- Perceptions and satisfaction with mobile app (sample of those randomized to intervention): We will qualitatively assess patient experience using the intervention using a semi-structured qualitative interview guide. [Appendix M]

Administration of self-report measures: We will collect and enter all patient-reported data electronically using Research Electronic Data Capture (REDCap). An RA will ask study participants to complete questionnaires in-person during clinic visits, via email, or over the telephone.

### 9.4 Long-Term Follow-Up Data Collection

We will collect demographic information, sexual function, QOL, mood, and usability of the mobile app (only in patients randomized to the intervention).

Participant	Baseline	8 weeks (+/- 1 week)	12 weeks (+/- 1 week)
Patient Measures:			
Demographics	X		
PROMIS Sexual Function and Satisfaction	X	X	X
Measure			
Functional Assessment of Cancer Therapy-Bone	X	X	X
Marrow Transplant (FACT-BMT)			
Hospital Anxiety and Depression Scale (HADS)	X	X	X

System Usability Scale (only intervention participants)		X	
Medical Record Review:			
Chart review from electronic health record	X		

## 10.0 Data and Specimen Banking: Not Applicable

## 11.0 Data Management and Confidentiality

11.1 Analysis **Data analysis Aim 1 (feasibility):** We will report baseline characteristics of all study participants. The primary endpoint of the proposed study is feasibility. The proposed intervention app will be deemed feasible if at least 60% (95% CI +/- 12%) of eligible patients are enrolled in the study, and of those enrolled, at least 60% engage with at least 70% of the intervention modules (modules engagement will be captured by the app). The 60% feasibility and intervention module completion cut-off is commonly used in behavioral intervention studies. We will also use descriptive statistics to examine the usability of the mobile app based on the system usability scale.

Data analysis Aim 2 (preliminary efficacy): We will compare patients' sexual function (PROMISE Sexual Function and Satisfaction), QOL (FACT-BMT), and depression (HADS) at week-8 and week-12 using analysis of covariance adjusting for baseline values. Mixed linear models will be fitted to adjust for selected demographic and clinical factors when examining change in outcomes of interest across all time points. We will also test for potential moderators of the intervention effect using interaction terms for the mixed linear models to assess whether differences in patient-reported outcomes are moderated by patient factors (age, gender, computer experience), or transplant type. We will use conservative (alpha=0.05) and liberal (alpha=0.25) values to assess statistical significance in this pilot study. When handling missing data, if data appear to be missing at random, we will employ multiple imputation. If data are not missing at random, we will employ pattern mixture modeling.

Data analysis Exploratory aim: We will analyze the qualitative data using a multi-step process using coding and content analysis to explore 1) patients' perceptions and satisfaction with the mobile app; 2) patients' opinions regarding the app content. This will involve coding to structure data into categories and creating groups according to the broader issues or themes. We will identify major and minor themes within each content area and we will extract and highlight messages. Two independent coders will examine discrepant, unexpected, or unclear data until agreement is reached. To assure the trustworthiness of our findings, we will take steps to maximize reliability and credibility including: investigator triangulation (using a multidisciplinary team of investigators), and team debriefs of the interview content.

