#### 3.0 Inclusion and Exclusion Criteria

We will recruit a total of 60 HCT survivors who are at least 3 months post-HCT and without evidence of disease from Massachusetts General Hospital Cancer Center and Dana-Farber Cancer Institute to participate in this randomized trial.

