## 6.0 Multi-Site Research: Not Applicable

## **7.0** Study Timelines

#### 7.1 Timelines

We anticipate that we will need approximately 2 years to enroll the sample size for this study. Participants will remain on the study for up to 1 year.

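### The week-8 and week-12 ANCOVA omits transplant type, a randomization stratum, and sections 9.1 and 9.2 name different strata

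*Combined protocol and SAP*

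**What the plan says.** **Analysis.** Section 11.1 (Aim 2) compares sexual function, QOL and depression "at week-8 and week-12 using analysis of covariance adjusting for baseline values". No other covariate is named for these comparisons. Mixed models across all time points adjust for demographic and clinical factors that are not listed. Transplant type is named in the analysis only as a possible moderator in those models. Significance is judged at alpha 0.05 and 0.25.

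**Randomization, section 9.1.** "We will conduct a single-site pilot randomized trial in 60 HCT survivors" opens the section. The reason for stratifying follows: "As transplant type is an important variable that affects sexual function and recovery post-HCT", and therefore "we will stratify by HCT type to ensure balanced representation between the study groups". No other stratification factor is named. Section 6.0 reads "Multi-Site Research: Not Applicable".

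**Randomization, end of section 9.2.** Allocation is done "using a computer-generated randomization schema, stratified by study site and transplant type". Neither section states a block size, minimization or any other balancing method.

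**Recruiting institutions.** Section 3.0 takes patients "without evidence of disease from Massachusetts General Hospital Cancer Center and Dana-Farber Cancer Institute to participate in this randomized trial". Sections 19.0, 22.2 and 23.0 name three institutions by adding Beth Israel Deaconess, whose patients come by clinician referral. Section 19.0 places the sexual health visit in the MGH clinic.

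**Sample size.** Section 11.2 claims more than 80% power for a 7-point difference in satisfaction with sex (SD 8, 60 patients). It also says the pilot data will serve to determine the effect size for later trials.

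**The concern.** The design treats transplant type as prognostic and the week-8 and week-12 comparisons ignore it. What follows depends on two things the documents leave open: how much transplant type predicts the later score once baseline is in the model, and whether allocation is balanced within strata.

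- If strata are balanced, stratification removes the between-stratum variance from the treatment contrast. The baseline-only ANCOVA leaves that variance in its residual, so its standard error overstates the true variability and the test runs below its nominal level.
- If strata are not balanced, the standard error and the test level are valid, but the estimate is noisier than an adjusted one.

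Either way, the pilot would hand a future trial intervals that are too wide or an estimate that is less precise than the data allow.

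The second issue needs no assumption. The two randomization descriptions do not name the same strata, so neither the person building the schema nor the person writing the analysis can tell which factors apply.

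**Working it through.** **1. The plan's own figure.** With 30 per arm, difference 7 and SD 8, the standard error is 8 × √(2/30) = 2.066, and 7 / 2.066 = 3.389. Two-sided power at 0.05 is Φ(3.389 − 1.960) = 92.3% by the normal approximation and 91.5% by the noncentral t. This agrees with the stated >80%.

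**2. Formula for balanced strata.** Let s be the share of post-baseline variance due to transplant type. The baseline-only model estimates variance 4σ²/N for the treatment effect; the true variance is 4σ²(1 − s)/N. The SE ratio is therefore 1/√(1 − s).

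- s = 5%: 2.6% too large, type I error 4.5% at nominal 5%
- s = 10%: 5.4% too large, type I error 3.9%
- s = 20%: 11.8% too large, type I error 2.9%

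**3. Simulation.** 100,000 trials per scenario compared ANCOVA on baseline only with ANCOVA on baseline plus transplant type.

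- *From the protocol:* N = 60, 1:1 allocation, 7 points, SD 8, alpha 0.05 and 0.25.
- *Assumed:* s, half the patients autologous, SD 8 as the post-baseline residual SD, blocks of 4, two-sided tests.

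Full sample, blocks within transplant type (SE excess and type I error are for the baseline-only model):

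| s | SE excess | Type I at 5% | Type I at 25% | SD of estimate, without / with type | Power, without / with type |
|---|---|---|---|---|---|
| 0% | 0% | 5.1% | 24.9% | 2.08 / 2.09 | 91.0 / 91.0% |
| 5% | 2% | 4.5% | 24.1% | 2.04 / 2.04 | 91.5 / 92.3% |
| 10% | 5% | 4.0% | 22.5% | 1.98 / 1.98 | 92.0 / 93.5% |
| 20% | 11.5% | 3.0% | 20.0% | 1.87 / 1.87 | 93.1 / 95.8% |

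Full sample, unblocked (SE ratio 1.00 and nominal type I error at every share):

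| s | SD of estimate, without / with type | Power, without / with type |
|---|---|---|
| 0% | 2.11 / 2.13 | 90.5 / 90.0% |
| 5% | 2.10 / 2.07 | 90.6 / 91.4% |
| 10% | 2.10 / 2.01 | 90.6 / 92.8% |
| 20% | 2.11 / 1.90 | 90.7 / 95.3% |

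With 30% autologous instead of 50%, results at the 10% and 20% shares are nearly the same.

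**4. Single-sex endpoints** (erectile function, lubrication, vaginal comfort). Neither description stratifies by sex, so balance by transplant type is not forced within men or within women. With an assumed 30 of 60 patients and blocking within type, the SE excess is 0/2/2/5% at shares 0/5/10/20%, and type I error is 5.0/4.7/4.6/4.1% at nominal 5%. At the 20% share the SD of the estimate is 2.87 without and 2.72 with transplant type, so both effects are present in part. Unblocked, the SE is valid and the SDs are 3.04 and 2.77.

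**5. Second simulation with other settings.** Here SD 8 was the total SD, the baseline–outcome correlation was assumed to be 0.5, and each cell had 6,000 trials. With balanced strata and shares of 10/20/30%, mean model SE over true SD was 1.803/1.716 = 1.05, 1.800/1.638 = 1.10 and 1.804/1.517 = 1.19. Type I error was 3.8/3.0/1.9%. Adding transplant type brought it back to about 5%.

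**6. The strata side by side.** Section 9.1: transplant type, single-site. Section 6.0: multi-site not applicable. Section 9.2: study site and transplant type. Section 3.0: two institutions. Sections 19.0, 22.2 and 23.0: three. Holding the study visit at MGH may explain the term single-site. It does not explain two different lists of strata.

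**The case against.** **The prognostic strength is unknown.** Baseline adjustment may already absorb much of what transplant type would explain, and at a 5% share the effect is negligible. This stands, and it is why the size can be given only as a range.

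**Unblocked allocation would defeat section 9.1's stated aim of balance**, so the lost-precision case is less likely in the full sample. This largely stands. The single-sex endpoints still show part of that loss under blocking.

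**With balanced strata, adding transplant type does not improve the full-sample point estimate.** This is correct: the SDs with and without it are practically equal. The gain there is an honest standard error and a test at its nominal level.

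**The mixed models already deal with it.** A conventional interaction model includes the main effect of transplant type, so the moderator models would contain it. That does not change the ANCOVA, which is specified separately.

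**The single-sex absolute figures are borrowed.** The 7 points and SD 8 belong to satisfaction with sex, and the other domains use different scales. This stands for absolute SDs and power. The relative SE excess and type I error do not depend on the scale.

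**Section 9.1 does not say that transplant type is the only stratum**, and section 9.2 may simply be the fuller text. That is possible, but a reader cannot know it, and the single-site statements point the other way.

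**Conclusion.** Both points hold, and both are minor. The omission of transplant type from the ANCOVA and the mismatch in strata are certain from the text. The numerical effect of the omission is conditional on an assumed share of post-baseline variance:

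- none at 0% and negligible at 5%
- at 10% to 20% with balanced strata, standard errors 5% to 11.5% too large in the full sample
- at 20% without balance, an SD of 2.11 where 1.90 was available

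The error is in the conservative direction. The treatment estimate is not biased, false positives are not inflated, power for satisfaction with sex is at least 90% in every full-sample scenario, and the primary feasibility endpoint does not use this model. What is affected is the precision reported for the secondary comparisons that are meant to inform a later trial. The strata mismatch has no demonstrated numerical consequence, but it leaves both the schema and the correct analysis undefined.

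**What to change.** 1. In section 11.1, add transplant type as a fixed covariate to the week-8 and week-12 ANCOVA for every endpoint, including the single-sex ones. Name it as a main effect in the mixed models.
2. Make sections 6.0, 9.1 and 9.2 state one set of sites and the stratification factors actually used, and say how allocation is balanced within strata.
3. If site is a stratum, add it to the full-sample models, for example as MGH versus other. In simulations with an assumed 60/30/10 site split and a non-prognostic site, this cost about 0.1 points of power in the full sample. It cost about 1 point (up to 2) in a single-sex subset of 30, so adjusting those models for baseline and transplant type only is a reasonable compromise. This coding choice is secondary to items 1 and 2.

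The change is to protocol and SAP wording and should be made before outcome data are examined. It uses one degree of freedom, or two with site. If transplant type turns out not to be prognostic, the loss is 0 to 0.5 points of power in the full sample and about 1 to 2 points in a single-sex subset of about 30.
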